8.1.2 Secondary Endpoints

8.1.2.1 Hypothesis 1- Oncolytic adenovirus-mediated cytotoxic and IL-12 gene therapy has an effect on serum PSA levels.

Serum PSA will be assessed according to Table 7 and compared to the subject's baseline value.

8.1.2.2 Hypothesis 2- Oncolytic adenovirus-mediated cytotoxic and IL-12 gene therapy has an effect on PSADT.

Serum PSA will be assessed according to Table 7. PSADT will be determined by logarithm regression analysis as described previously (38). PSADT prior to the study therapy will be calculated using a minimum of three PSA values including the last PSA prior to initiation of the study therapy. Subjects who do not have at least three pre-treatment PSA values will be excluded from the analysis. PSADT after the study treatment will be calculated from the nadir and will use all PSA values prior to the implementation of additional salvage therapy such as ADT.

PSADT will be calculated assuming first-order kinetics using the following equation:

$$\ln(\text{PSA}) = \beta_0 + \beta_1 t$$

where β_0 is the point where the regression line crosses the ordinate at $t = 0$ and β_1 is the number of units that $\ln(\text{PSA})$ changes for every one-unit change in time (i.e., the slope). PSADT is defined as $\ln(2) / \beta_1$. Data are evaluated for normality the ranked data are considered if data are not normal.

8.1.2.3 Hypothesis 3- Oncolytic adenovirus-mediated cytotoxic and IL-12 gene therapy has no significant effect on quality of life.

We will use two instruments to measure QOL: EPIC and EQ-5D. QOL instruments will be collected on all subjects at baseline, 6, 12 and 24 months after the adenovirus injection.

EPIC questionnaires will be completed by the subject. The questionnaires will be summarized into three endpoints of function and bother in urinary, bowel and sexual domains with a score of 0 to 100. EQ-5D will have a self-report score of 1 to 3 in five domains (mobility, self-care, usual activity, pain/discomfort and anxiety/depression), and an overall health score 10 to 100. If a subject death is related to prostate cancer or the study treatment, the worst score will be given and the subject will be included in the analysis.

Data will be evaluated for normality, data transformation or nonparametric approach will be considered if data are not normal.

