For each QOL domain variable, analysis of variance and covariance (ANCOVA) will be used. Analysis will include the baseline covariates of pre-treatment domain score, covariate of time (of assessment post-treatment) and the independent

treatment variable. The analysis will start testing for treatment by time interaction, followed by testing the treatment effect at each time point if the interaction is detected at critical value 0.10, or testing the overall treatment effect or time effect at critical value of 0.05 if otherwise.

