8.3 Statistical Analysis

Analysis for this phase 1 trial will be descriptive. We will report all toxicity results taking into account any baseline abnormalities.

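### Section 8.1.2.3 runs an unadjusted testing sequence on each of 9 to 12 QOL scores under one no-effect hypothesis, although section 8.3 calls the analysis descriptive

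*Combined protocol and SAP*

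**What the plan says.** Quality of life is a secondary objective (section 2.2.5). Section 8.1.2.3 gives it one hypothesis: "Oncolytic adenovirus-mediated cytotoxic and IL-12 gene therapy has no significant effect on quality of life".

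The same section lists the scores:
- EPIC is "summarized into three endpoints of function and bother in urinary, bowel and sexual domains with a score of 0 to 100".
- The second instrument, the EQ-5D, contributes five items, each rated from 1 to 3, "and an overall health score 10 to 100".

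Both instruments are completed at baseline and at 6, 12 and 24 months.

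A separate ANCOVA is planned for each QOL domain variable, with the baseline score, post-treatment assessment time and treatment as terms. The treatment-by-time interaction is tested first, at 0.10. If it is detected, treatment is tested at each time point, with no level given. If it is not, the plan goes on to "or testing the overall treatment effect or time effect at critical value of 0.05 if otherwise".

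No score or visit is named as deciding, and there is no hierarchy and no adjustment. Section 8.3 says: "Analysis for this phase 1 trial will be descriptive".

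**The concern.** One hypothesis is attached to many tests, and the plan does not say how their results combine. If one score of 12 is significant, the reader cannot tell whether Hypothesis 3 has been refuted. If none is, the wording invites the statement that the therapy does not affect quality of life. The stated 0.05 is the error rate of neither conclusion.

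The section also conflicts with 8.3: a decision path with critical values is not a descriptive analysis, so both cannot govern the QOL report. At stake is how a secondary endpoint is read. Dose escalation, the MTD and the stopping rules do not use QOL.

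**Working it through.** The plan states no error rate or power for QOL, so there is no figure of its own to reproduce.

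**Inputs from the documents.** Three EPIC domains; five EQ-5D items and one overall health score; three post-baseline visits; 0.10 for the interaction and 0.05 for the overall tests (8.1.2.3). Five dose cohorts of 3 to 6 men, 15 to 30 in all, every man injected (5.1.2.5 and 8.2).

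**Assumptions, not in the documents.** Two-sided tests; 0.05 for the per-visit tests; between-score correlation varied; within-man correlation between visits 0.5; normally distributed, complete data.

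**Step 1, number of scores.** With one EPIC score per domain: 3 + 5 + 1 = 9. With function and bother separate: 6 + 5 + 1 = 12.

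**Step 2, one 0.05 test per score, independent scores.** The chance of at least one false positive is 1 − 0.95^k.
- k = 9: 1 − 0.95^9 = 37%.
- k = 12: 1 − 0.95^12 = 46%.
- EPIC domains alone, k = 3: 1 − 0.95^3 = 14%.

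**Step 3, the same with correlated scores** (400,000 simulated draws of k equally correlated z-tests).

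| Correlation | 9 scores | 12 scores |
|---|---|---|
| 0.5 | 27% | 32% |
| 0.7 | 20% | 23% |
| 0.9 | 12% | 14% |

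Even at 0.9 the rate is more than twice 0.05.

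**Step 4, time-effect test only.** This needs no control arm. Simulated with 12 scores and no true change, the chance of at least one significant score is about 20% at correlation 0.8, 33% at 0.5 and 43% at 0.2.

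**Step 5, the full rule, with dose cohort assumed to be the treatment variable.** Interaction at 0.10; if detected, any of three per-visit cohort tests at 0.05; otherwise the overall cohort or time test at 0.05. The baseline covariate was left out. About 11% of individual scores are falsely positive. With 12 scores the chance of at least one is about 42% to 75% for correlation 0.8 to 0.2, and about 63% at 0.5; cohorts of 3 and of 6 give nearly the same result. With 9 scores it is about 55% at 0.5. If only cohort effects count and time effects do not, the 12-score rate is about 37% to 62% for correlation 0.7 to 0.

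**Step 6, what non-significance would show.** Take a one-sample t-test of mean change at 0.05, with a true shift of 0.5 standard deviations (assumed). Power is 44% with 15 men and 75% with 30. The 95% interval for a mean change has half-width t/√n in standard deviation units: 2.145/√15 = 0.55 with 15 men and 2.045/√30 = 0.37 with 30. A non-significant result is therefore compatible with a sizeable deterioration.

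**The case against.** The strongest reply is that familywise type I error is the wrong yardstick here. Hypothesis 3 claims no effect, so the harmful mistake is to miss a real deterioration, and unadjusted tests make a no-effect claim harder to sustain. This stands, and it decides the remedy. A reader might infer that a Holm adjustment is needed. With a shift of 0.5 standard deviations, Holm's first step at 0.05/12 would cut power from 44% to 12% with 15 men and from 75% to 38% with 30. False reassurance would become more likely, and the section would still not be descriptive. What does not follow is that the present rule is harmless: a chance positive on some score is likely, and the plan gives no way to read it.

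A reader might also infer that a fixed share of such trials would report a false QOL effect. The documents do not support any single figure. They give no correlation between scores and no level for the per-visit tests. With no control arm, the treatment term has no meaning unless it is read as dose cohort; that is a more basic gap, and the upper range in step 5 depends on that reading. The simulations also omit the baseline covariate and treat three-level EQ-5D items as normal, although the section allows transformation or a nonparametric approach. The exact percentages are therefore illustrative.

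Finally, this is a secondary endpoint of a phase 1 study that makes no power claim. That limits the weight of the point, but does not remove the contradiction between 8.1.2.3 and 8.3.

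**Conclusion.** The point holds as a matter of wording and interpretation. Section 8.1.2.3 attaches critical values to 9 to 12 scores under one hypothesis and gives no rule for combining them, while 8.3 promises description only. Under every assumption tried, the chance of at least one spurious significant score exceeds 0.05. The time-test range of about 20% to 43% is the firmer one, because it needs no treatment contrast; the 42% to 75% range requires dose cohort to be the treatment variable and 0.05 to apply at each visit. In the other direction, 15 to 30 men cannot establish absence of effect through non-significance.

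The documents do not support extending this to the toxicity or MTD conclusions. The consequence is modest, and the change is worth making because it is cheap.

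**What to change.** In section 8.1.2.3:
- Delete the sequence of interaction, per-visit and overall tests with its critical values.
- State that change from baseline in every EPIC and EQ-5D score will be reported at 6, 12 and 24 months as an estimate with a 95% confidence interval, labelled descriptive, with no significance claim.
- Say whether EPIC function and bother are scored separately, so that the list of scores is fixed.
- Reword Hypothesis 3 as an aim to describe change in quality of life after the therapy. Section 2.2.5 needs no change, and the section then agrees with 8.3.

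If the sponsor wishes to keep a test, it should be one contrast (score, visit and comparison) of the sponsor's choosing, named in advance, with everything else descriptive. Holm adjustment should not be used to support a claim of no effect.

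The cost is a wording change, with no new data, visits or subjects. The downside is that, without a pre-named contrast, no QOL change can be declared statistically significant.

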8.1.3 Exploratory Hypothesis

8.1.3.1 Hypothesis- There is a possible association between the primary and secondary outcomes and immunological endpoints including serum IL-12 and IFN- γ levels, and NK cell cytolytic activity. Immunological measurements, as continuous variables, will be collected from blood at baseline and at specified times after the adenovirus injection.

Each variable will be evaluated for the proportional hazard assumption. Data will be categorized if the assumption is not met. Cox regression models will be used to study the association of baseline and post-treatment variables, respectively, with outcome. The analysis will begin testing the individual variable effect including testing for treatment by individual variable interaction, followed by multivariable analysis. The variable with individual effect at 0.05 level or variable interaction at 0.10 will remain in the final multivariable model with assessment of goodness-of-fit (e.g. ROC).

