1.2.2.1.2 Short-term Results

There were no dose-limiting toxicities (DLTs) or serious adverse events (SAEs). Ninety-four percent of the AEs observed were mild or moderate (grade 1/2) in nature. There were nine (6%) grade 3 events including four events of hyperglycemia, and one event each of cardiac ischemia, dyspnea, hypermagnesemia, lymphopenia, and neutropenia. All subjects exhibiting grade 3 hyperglycemia were diabetics. The one event of grade 3 cardiac ischemia occurred in a subject with a history of heart disease. The one event of grade 3 dyspnea occurred in a subject with a history of chronic obstructive pulmonary disease. The grade 3 events of hypermagnesemia, lymphopenia, and neutropenia each occurred in a single subject and were transient. There were no grade 4 events.

Seven of 16 (44%) subjects demonstrated a > 25% decrease, and 3 of 16 (19%) demonstrated a > 50% decrease, in serum PSA lasting < 120 days. There was excellent correlation between persistence of the Ad5-CD/TKrep adenovirus, as determined by viral DNA in blood, and PSA response. Transgene expression and tumor destruction at the injection site were confirmed by needle biopsy at 2 weeks. Two subjects were negative for adenocarcinoma at 1 year.

Ad5-CD/TKrep DNA was detected in blood as far out as day 76. No infectious adenovirus was detected in serum or urine at any time point. All subjects developed high titers of NAB to adenovirus.

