1.2.2.1.3 Long-term Results

Long-term outcome was assessed at 5 and 7 years. At 5 years, PSA doubling time (PSADT) and delay in the administration of additional salvage therapy was examined (38). At 7 years, overall (OS) and disease-specific (DSS) survival were compared to well-matched historical controls (41).

When considering all evaluable subjects ($n = 14$), PSADT increased from a mean of 17 months (prior to gene therapy) to 31 months (after gene therapy) ($P = 0.014$) (**Table 2**). A greater percentage of subjects who received the highest adenovirus dose exhibited an increase in PSADT suggesting a dose-dependent effect. Assuming that salvage androgen deprivation

therapy (ADT) would have been initiated at a PSA of 15 ng/mL, administration of the gene therapy delayed the projected onset of salvage ADT by a mean of 2.2 years in all evaluable subjects and 2.6 years in subjects receiving the highest adenovirus dose.

Table 2. 5-Year Analysis in Locally Recurrent Setting

Subject cohort	Mean PSADT		Delay in Salvage ADT ²
	Before GT (months)	After GT (months)	
All evaluable subjects (n = 14) ¹	17	31	26 months (2.2 years)
Highest Ad dose subjects (10^{12} vp; n = 6)	18	32	31 months (2.6 years)
Subject cohort	Subjects who exhibited increase in PSADT		
Two lowest Ad dose cohorts (10^{10} and 10^{11} vp)	3 of 8 (38%)		
Highest Ad dose cohort (10^{12} vp; n = 6)	5 of 6 (83%)		

¹PSADT after the gene therapy could not be determined in two subjects owing to a non-treatment-related death, and implementation of salvage ADT 2 months after gene therapy at subject's request.

²The delay in administration of salvage ADT was determined by calculating when the PSA would have crossed a threshold of 15 ng/mL using pre-gene therapy versus post-gene therapy PSADT.

OS and DSS were examined at 7 years and compared to well-matched historical controls (Figure 1 and Table 3). The control cohort included 154 patients with locally recurrent prostate cancer treated at the University of Michigan between 1986 and 2000 (52). At 7 years, OS was 69% vs. 44% ($P = .07$), and DSS was 94% vs. 55% ($P = .03$), in the gene therapy vs. the control cohort, respectively. Median survival was 8.6 vs. 5.9 years in the gene therapy vs. the control cohort, respectively.

[figure not shown]

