1.2.2.3.2 Results

hNIS reporter gene expression (i.e., ^{99m}TcO₄ uptake) was detected in 0 of 3 (0%) subjects at 1×10^{11} vp, 6 of 8 (75%) subjects at 1×10^{12} vp, and 6 of 6 (100%) subjects at 5×10^{12} vp. Gene expression was readily detected in the prostate following injection of 1×10^{12} vp and 5×10^{12} vp (Figure 2). Serial imaging on consecutive days demonstrated that gene expression in the prostate lasted ≤ 7 days (Figure 3).

Importantly, whole body planar scans demonstrated that no reporter gene expression was detected outside of the prostate in any subject (Figure 4).

[figure not shown]

Figure 2. Non-invasive imaging of gene expression in the prostate. The subject received an intraprostatic injection of 5×10^{12} vp of the Ad5-yCD/mutTK_{SR39}rep-hNIS adenovirus on day 1. 16 mCi Na^{99m}TcO₄ was administered on days 2 and 3 and SPECT was performed 4 hours later. Day 3 images are shown. Radiotracer uptake is indicated by the colors (yellow > red > green). Activity in the urinary bladder (UB) is due to excretion of the radiotracer through that organ. Activity in the penis (Pe) is due to blood flow

through that organ. Activity in the bowel (Bo) is due to trapping. L, left; R, right; P, posterior; A, anterior.

[figure not shown]

Figure 3. Persistence of gene expression in the prostate. A subject with intermediate-risk prostate cancer received an intraprostatic injection (right side only) of Ad5-*yCD/mutTK_{SR39}rep-hNIS* (1×10^{12} vp) on day 1. $\text{Na}^{99m}\text{TcO}_4$ (16 mCi) was administered on days 2, 3, 4 and 8 and SPECT imaging (whole body and pelvic planar scans, pelvic SPECT) commenced 4 h later. hNIS gene expression (i.e., $^{99m}\text{TcO}_4^-$ uptake) was detected in the right side of the prostate on all days. L, left; R, right; P, posterior; A, anterior.

[figure not shown]

Figure 4. Whole body distribution of $^{99m}\text{TcO}_4$ uptake. A subject with intermediate-risk prostate cancer received an intraprostatic injection of Ad5-*yCD/mutTK_{SR39}rep-hNIS* (1×10^{12} vp) on day 1. $\text{Na}^{99m}\text{TcO}_4$ (16 mCi) was administered on day 4 and SPECT imaging commenced 4 h later. Shown are whole body planar scans prior to (pre-injection) and three days after (post-injection) the adenovirus injection. Activity in the salivary glands (Sal), lachrymal glands (Lac), thyroid gland and stomach are due to endogenous hNIS

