IL-12 has demonstrated significant anti-tumor activity in preclinical models including prostate cancer (61). However, its activity in the clinic has been modest when administered as a recombinant protein or expressed from retrovirally-transduced fibroblasts (59). Furthermore, IL-12 has resulted in severe toxicity including two treatment-related deaths when administered systemically as a recombinant protein (62, 63). We believe that IL-12 produced by a locally administered, oncolytic adenovirus may exhibit better activity in the clinic without excessive toxicity relative to previous approaches. Administering the adenovirus intraprostatically (rather than systemically) should result in a high, local concentration of IL-12 within the prostate. This should limit systemic toxicity and promote IL-12's anti-tumor effects. IL-12 has been well-tolerated in humans when administered locally (59). Moreover, we believe our multi-modal approach may function like an autologous, whole tumor

vaccine. All modalities (*oncolytic viral therapy, cytotoxic gene therapy, IL-12 gene therapy, and radiotherapy* when combined with radiation) result in significant tumor cell destruction and the release of tumor antigens. This may facilitate antigen cross-presentation by professional APCs, which, when coupled with IL-12's ability to promote Th1 differentiation, may lead to the development of antigen-specific, cell-mediated immunity.

We have demonstrated in a preclinical model of prostate cancer that the addition of IL-12 to our therapeutic platform improves both local and metastatic tumor control that is mediated by both the innate and adaptive arms of immunity (57).

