2.2 Secondary

To assess:

2.2.1 PSA response.

2.2.2 Freedom from biochemical/clinical failure (FFF).

2.2.3 PSA doubling time (PSADT) before and after administration of the study therapy.

2.2.4 Disease-specific and overall survival.

2.2.5 Quality of life (QOL).

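### The planned serum IL-12 analysis has no viral DNA term and no stated dose effect, so a link with outcome could partly or wholly reflect virus exposure

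*Combined protocol and SAP*

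**What the plan says.** Objective 2.3.1 and Section 8.1.3.1 name the same explanatory variables: the plan looks for a "possible association between the primary and secondary outcomes and immunological endpoints including serum IL-12", IFN-γ and NK cell activity. Each variable is first tested alone in a Cox model, together with its interaction with *treatment*. Those passing at 0.05 (0.10 for an interaction) go into a final multivariable model. *Treatment* is not defined, and the trial has one arm with five adenovirus doses (Table 5). The outcomes covered include "2.2.1 PSA response" from the secondary objectives. Section 8.3 calls the trial's analysis descriptive.

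Viral DNA in blood is measured at each scheduled draw until two results in a row are negative (6.1.4, 6.2.5). Serum IL-12 follows the same rule (6.1.5, 6.2.6). Viral DNA then appears in no objective in Section 2 and nowhere in Section 8.

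Trial 1 studied the same disease with a related virus; Section 5.1.2.8 says the earlier viruses lacked IL-12. Section 1.2.2.1.2 reports: "There was excellent correlation between persistence of the Ad5-CD/TKrep adenovirus, as determined by viral DNA in blood, and PSA response". On dose, Section 1.2.2.1.3 adds: "A greater percentage of subjects who received the highest adenovirus dose exhibited an increase in PSADT suggesting a dose-dependent effect".

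**The concern.** The documents supply both halves of a confounding path. Virus leads to IL-12, because the vector carries the human IL-12 gene (5.1.2.1). Virus may also lead to PSA outcome without IL-12, because Trial 1 saw that relation with a vector that had no IL-12 gene. A man with more, or longer-lasting, virus could have both higher serum IL-12 and a better PSA course, even if IL-12 did nothing.

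IL-12 is the component this trial adds, and 8.1.3.1 is the only planned analysis of serum IL-12 against outcome. As written, the report could not show whether an IL-12 association is more than virus persistence or dose would produce. The data that would help are already being collected.

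**Working it through.** **1. What is measured and what is analysed**

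| Variable | Collected | Role in Section 8 |
|---|---|---|
| Serum IL-12, IFN-γ | Each draw until two negatives in a row | Explanatory variables in 8.1.3.1 |
| NK activity | Each draw in the first two weeks | Explanatory variable in 8.1.3.1 |
| Viral DNA | Same rule as IL-12 | None |
| Dose | Assigned, 10^10 to 10^12 vp | Not named; possibly the undefined *treatment* |

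**2. Sample size.** Five cohorts of 3 to 6 give 5 × 3 = 15 and 5 × 6 = 30, which reproduces Section 8.2.

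**3. Strength of the Trial 1 evidence.** The viral DNA statement rests on 16 men, with no coefficient and no reported link with time to failure. The PSA falls were short: 3 of 16 men "demonstrated a > 50% decrease, in serum PSA lasting < 120 days". For dose, PSA doubling time rose in 5 of 6 men at the top dose and 3 of 8 at the lower doses. The odds ratio is (5 × 5)/(1 × 3) = 8.3. Two-sided Fisher p = (1 + 48 + 336 + 28)/3003 = 413/3003 = 0.14, so the dose signal is suggestive only.

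**4. How a spurious link arises.** Let persistence V have hazard ratio HR per SD, let serum IL-12 have correlation ρ with V, and give IL-12 no effect. To first order, IL-12 alone then shows a log hazard ratio of ρ × ln(HR):
- ρ 0.3, HR 0.7: 0.3 × (−0.357) = −0.107, apparent HR 0.90
- ρ 0.7, HR 0.5: 0.7 × (−0.693) = −0.485, apparent HR 0.62
- ρ 0.9, HR 0.35: 0.9 × (−1.050) = −0.945, apparent HR 0.39

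**5. How often IL-12 passes the screen.** Every HR and ρ here is an assumption; the documents give neither. Set-up: exponential times, 20% censored, Cox Wald test of IL-12 at two-sided 0.05, 2,000 trials per setting (Monte Carlo standard error at most √(0.25/2000) = 1.1 points). The outcome is PSA failure and IL-12 has no effect.

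| Setting | 15 men | 30 men |
|---|---|---|
| ρ 0 | about 5% | about 5% |
| ρ 0.3, HR 0.7 to 0.35 | 7–10% | 7–16% |
| ρ 0.7, HR 0.5 | 21% | 46% |
| ρ 0.9, HR 0.35 | 58% | 91% |

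Repeat runs at the middle setting gave 20–23% and 44–47%; a likelihood-ratio test gave 25% and 50%. For PSA response at Trial 1's rate (7 of 16; HR 1.43 to 2.86; 700 trials per setting), IL-12 passed in 4–44% (15 men) and 6–82% (30 men).

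**6. Adding persistence.** With V entered as five equal ordered groups, the PSA-failure rates fall to 5–7% (15 men) and 5–12% (30 men), and the PSA-response rates to 3–6% and 5–10%. This depends on how men spread across groups. If 70% share the top group (assumed), IL-12 still passes with 30 men in 16–17% (ρ 0.7, HR 0.5) and 46–48% (ρ 0.9, HR 0.35).

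**7. Dose in place of persistence.** A separate run of 1,500 trials per setting let both IL-12 and outcome depend on log dose (ρ 0.5 to 0.9, HR 0.7 or 0.5 per SD). IL-12 passed in 8–47% (15 men) and 14–81% (30 men) without dose in the model, and in about 4–7% with it.

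**The case against.** The strongest reply is that the plan never claims IL-12 acts independently of the virus. It looks for a possible association, and an association that runs through virus amount is still an association. This stands. A reader might infer that 8.1.3.1 produces false findings or states something untrue. The documents do not support that reading; the gap limits what a positive result could mean.

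Second, *treatment* may mean dose, the only treatment factor planned to differ between men, and an interaction model normally carries its main effect. This partly stands. The plan does not say so, and viral DNA is absent on either reading, but it would be too strong to say that dose is definitely left out.

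Third, the IL-12/virus correlation may be weak. Section 1.3 expects that intraprostatic delivery "should result in a high, local concentration of IL-12 within the prostate". In Trial 1 viral "DNA was detected in blood as far out as day 76", while in Trial 4 "Serial imaging on consecutive days demonstrated that gene expression in the prostate lasted" 7 days or less. DNA in blood may therefore outlast gene expression, and at correlation 0.3 the rates lie close to 5%. This stands, and it means no single figure from the simulations describes this trial.

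Fourth, adjustment cannot settle the question. Every man receives an IL-12 vector, there is no control arm, and viral DNA may itself partly result from IL-12. This also stands. The adjusted estimate is informative mainly if the association survives.

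**Conclusion.** A minor point and a cheap improvement. The documents establish that 8.1.3.1 has no viral DNA term and no stated dose main effect, that the virus is a source of IL-12, and that a related virus without IL-12 showed persistence tracking PSA response. An IL-12/outcome association could therefore partly or wholly reflect virus exposure. The MTD and the day-30 toxicity results are unaffected.

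The size is unknown. It runs from near the nominal 5% if serum IL-12 and virus are weakly correlated to very high if both the correlation and the virus effect are strong, and the range mainly reflects the assumed inputs. A reader might also infer that adding viral DNA restores an error rate near 5%. That holds roughly when men are spread evenly over the persistence groups, but not when most share one group.

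**What to change.** In 8.1.3.1, for PSA response, PSA failure and survival, report the IL-12 estimate with its confidence interval three ways: alone, with dose level (log vp) added, and with a viral DNA summary added. Use the last positive draw up to month 1, and avoid one dominant top group where the data allow finer coding.

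Fit all three on the same men from the same month-1 starting point, with IL-12 also summarised from draws up to then, so that they differ only by the added covariate. PSA is drawn weekly in the first two weeks (Table 7), so a response can precede the month-1 viral summary. In this comparison, count only PSA responses after month 1, or label the PSA-response part descriptive.

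State that an association lost on adding viral DNA is inconclusive, and that confounding remains if many men share one persistence group. Add one table by dose level: proportion PCR-positive at each visit, last positive draw, and PSA response by last positive draw. Keep the analysis now planned in 8.1.3.1, the day-30 toxicity analysis and the 6.6 definitions unchanged.

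The cost is analysis text and one table; no new samples, assays or visits. The downside is precision. If IL-12 truly has HR 0.5 per SD, virus has no effect and the correlation is 0.7, adding persistence cuts power from about 46% to 30% with 15 men and from about 83% to 61% with 30. At correlation 0.9 it falls from 43% to 16% and from 83% to 36%. These runs start at injection and keep all men, so the month-1 start could cost somewhat more.
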